2.4.3.2 Baseline Visit

The investigators provided participants with postoperative recovery education and collected data on demographic information, clinical characteristics, assessment scales, and routine examinations.

2.4.3.3 Abdominal acupuncture treatment

The initial abdominal acupuncture treatment was performed 4–6 hours after surgery, followed by one session daily from postoperative day 1 through day 4, yielding a total of five sessions per treatment course. Throughout the treatment period and thereafter, patients' clinical conditions were systematically recorded and evaluated, with concurrent monitoring of adverse events and concomitant medication use.

2.4.3.4 Aftertreatment Visit

On the 14th day following the final treatment, a quality-of-life assessment was conducted, and individualized recommendations were provided based on the patient's current condition.

2.4.3.5 Patient Withdrawals

Patients may leave the study at their own discretion, and the investigator may determine if the patients withdraw from the trial due to violation of the trial protocol or the occurrence of a serious adverse event. Figure 1 shows the flow diagram of the trial.

[figure not shown]

Figure 1 Flow chart

2.4.4 Sample Size

This study was designed as a randomized controlled trial, with the treatment group receiving abdominal acupuncture and the control group receiving conventional therapy. The primary outcome measure was the time to first postoperative flatus. Based on published literature, the mean \pm standard deviation of the time to first flatus in the control group was 37.60 ± 4.11

hours. It was anticipated that abdominal acupuncture would reduce this time by approximately

8.1 hours. Assuming a two-sided $\alpha = 0.05$ and a statistical power of 90%, the sample size was

$$n = \frac{2(z_\alpha + z_\beta)^2 * \sigma^2}{\delta^2}$$

calculated using the standard formula:

The required sample size was determined to be 33 participants per group. With a 1:1 randomization ratio, both the abdominal acupuncture group and the control group required 33 participants each. Allowing for a potential 15% dropout or loss to follow-up, the minimum enrollment target was set at 38 participants per group, resulting in a total sample size of no fewer than 76 participants.

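### The protocol's own formula and inputs give 6 patients per group, not the stated 33, so the standard deviation, difference, power and sample size do not fit together

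*Protocol*

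**What the plan says.** All the relevant text is in Protocol section 2.4.4 (Sample Size).

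- Endpoint: "The primary outcome measure was the time to first postoperative flatus".
- Variability, from published literature: "time to first flatus in the control group was 37.60 ± 4.11" hours.
- Effect: "It was anticipated that abdominal acupuncture would reduce this time by approximately" 8.1 hours.
- Error rates: two-sided alpha 0.05 and 90% power, with 1:1 allocation.
- Formula: n = 2(z_α + z_β)²σ²/δ² per group.
- Result: "The required sample size was determined to be 33 participants per group".
- Loss allowance: "Allowing for a potential 15% dropout or loss to follow-up, the minimum enrollment target was set at 38 participants per group", hence at least 76 in total.

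The protocol gives no other standard deviation, effect size, margin or adjustment that would enter the calculation.

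**The concern.** A reduction of 8.1 h against a standard deviation of 4.11 h is a standardised effect of 8.1/4.11 = 1.97. An effect that large needs only a handful of patients per group, so 33 at 90% power cannot be right on sight.

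This paragraph is the only justification for the trial's size. As printed, a reader cannot tell which effect the trial was built to detect. If 4.11 h and 8.1 h are right, the trial enrols more than five times what its target needs and the stated 90% power is false. If 33 and 8.1 h are right, the standard deviation is understated by a factor of about 2.5 and the assumed effect is about 0.8 standard deviations, not 1.97. If 33 and 4.11 h are right, the target difference was about 3.3 h, not 8.1 h. These are three different trials in terms of what a positive or negative result would mean.

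**Working it through.** **Inputs** (all from section 2.4.4): σ = 4.11 h, δ = 8.1 h, two-sided α = 0.05 (z = 1.960), power 90% (z = 1.2816), 1:1 allocation.

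**1. The protocol's formula with its own inputs**

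- (1.960 + 1.2816)² = 10.507
- σ² = 4.11² = 16.892; δ² = 8.1² = 65.61
- n = 2 × 10.507 × 16.892 / 65.61 = 354.98 / 65.61 = 5.41, so **6 per group**

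The stated 33 is not reproduced. It is 33/6 = 5.5 times the computed figure. An exact (noncentral t) calculation gives 86.7% power at 6 per group and 92.2% at 7, so 7 by that method.

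**2. Variants that might explain 33**

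| Variant | n per group (unrounded where known) |
|---|---|
| One-sided 0.05, 90% power | 4.4 |
| Two-sided 0.05, 80% power | 4.0 |
| Two-sided 0.05, 95% power | 6.7 |
| Two-sided 0.01, 90% power | 7.7 |
| Two-sided 0.01, 99% power | 12.4 |
| Mann–Whitney, relative efficiency 0.955 or 0.864 | 5.7 or 6.3 |
| Total N read as per-group n | 10.8 |
| σ not squared | 1.3 |
| Neither σ nor δ squared | 10.7 |
| δ not squared | 43.8 |

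None gives 33.

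**3. Power of 33 per group at the stated inputs**

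By the t-test, power for 8.1 h at σ = 4.11 h is above 99.99%.

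**4. What would give 33** (two-sided 0.05, 90% power)

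- Keeping δ = 8.1 h: σ = √(33 × 65.61 / (2 × 10.507)) = 10.15 h. The range that rounds up to 33 is about 10.0 to 10.15 h.
- Keeping σ = 4.11 h: δ = 4.11 × 3.2415 × √(2/33) = 3.28 h, or 3.33 h with the t distribution.
- Keeping δ = 8.1 h and letting only the acupuncture arm's standard deviation differ from 4.11 h: it would have to be about 13.8 h.

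As an illustration only, σ = 10.11 h gives n = 2 × 10.507 × 10.11² / 65.61 = 32.7, so 33. By the t-test, 33 per group then has 89.3% power and 32 has 88.4%. The value 10.11 h does not appear in the protocol.

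**5. Loss allowance**

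- Protocol's route: 33 × 1.15 = 37.95, so 38.
- Patients left after 15% loss: 38 × 0.85 = 32.3, below 33.
- Enrolment that leaves 33 after 15% loss: 33 / 0.85 = 38.8, so 39.
- Loss that 38 can absorb: (38 − 33)/38 = 5/38 = 13.2%.

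**The case against.** The strongest reply is that the mismatch does no demonstrated harm. On the printed inputs the trial is too large rather than too small. The type I error, the estimate and the analysis in section 7 are untouched. Section 2.4.2.1 gives recruitment as December 2023 to December 2024, so the size is probably settled. This is fair as to consequence: no loss of power or validity has been shown. It does not make the paragraph correct, because the stated power and n still contradict the stated inputs by more than fivefold.

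A second reply is that the document does not identify the faulty figure. That stands. A larger standard deviation is one explanation, a smaller difference is another, and a much more variable acupuncture arm is a third, though an unlikely one. The value 10.11 h is only an illustration. Equally, saying that 33 has 90% power for about 3.3 h describes the sensitivity of the trial; it does not explain how 33 was reached.

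A third reply is that n is not guaranteed to be adequate. This also stands, with a condition. If 8.1 h is kept and the true standard deviation were, say, 12 h (an assumption), the formula would need 46.1, so 47 per group, and 33 would have about 77% power.

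The loss allowance is a side remark. Multiplying by 1.15 is a common shortcut, the gap is one patient per group, and the protocol calls 38 a minimum.

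**Conclusion.** The concern holds. The stated 33 per group does not follow from the printed formula, standard deviation, difference, alpha and power, which give 6 (7 by exact t-test). The discrepancy is 5.5-fold, and the usual variants do not account for it. At the stated inputs the power of 33 per group exceeds 99.99%, so the stated 90% does not describe the stated design.

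This conclusion uses only figures in section 2.4.4 and takes 4.11 h as the common standard deviation, which is what the single σ in the formula implies. Which figure is wrong cannot be settled from the protocol. It needs correction because it is the sole basis for the size of the trial on its primary outcome. The case rests on the accuracy of the stated design, not on a shown lack of power.

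**What to change.** Go back to the literature source and the original calculation, and rewrite section 2.4.4 so that standard deviation, difference, alpha, power and n agree.

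- **If 4.11 h is the right standard deviation:** keep it and state that 33 evaluable patients per group have 90% power for a difference of about 3.3 h and over 99.9% for 8.1 h. State plainly that 33 exceeds what 8.1 h requires, and give the actual reason for choosing it.
- **If the standard deviation used was about 10.1 h:** replace 4.11 with the sourced value and keep 33. Note that the exact t-test power is then about 89%.
- **If the source shows something else:** recompute n from the sourced values and report the power that the enrolled number provides.

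In every case where 33 is kept, restate the loss allowance: 38 per group covers about 13% loss, and 15% needs 39.

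The cost is one paragraph of text. The stated power, difference or standard deviation will become a different figure. No patients are added in the first two cases; if 8.1 h is kept, this relies on the sourced standard deviation not exceeding about 10.1 h.

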2.4.5 Randomization

Randomization was performed using SPSS version 26.0. To ensure reproducibility of the randomization process, a Random Number Seed was first applied, followed by the generation of random numbers using the UNIFORM(Max) function. These random numbers were then used to assign participants into groups, and a randomization table was created accordingly. During clinical implementation, participants were allocated sequentially according to their order of enrollment by matching them to the corresponding numbers in the randomization table, and the designated treatment protocol was applied. In this study, the intervention group received abdominal acupuncture, while the control group received standard care.

3. Interventions

3.1 Basic treatment

The standardized postoperative management protocol consists of the following components:

- (1) Early oral intake: patients may commence a liquid diet 6 hours after surgery, advance to a semi-liquid diet following the passage of flatus, and transition to a regular diet after bowel movement.
- (2) Early mobilization: patients are encouraged to turn in bed and initiate physical activity as early as 6 hours postoperatively, and to ambulate as soon as their condition permits.
- (3) Adequate fluid supplementation.
- (4) Maintenance of fluid–electrolyte and acid–base balance.
- (5) Prophylactic antibiotic therapy to prevent infection.
- (6) Early removal of urinary catheters, drainage tubes, and other indwelling devices.
- (7) Postoperative analgesia: implementation of a multimodal pain management strategy.
- (8) In critically ill patients, supplemental oxygen and continuous electrocardiographic monitoring are required.

Note: During routine management, any interventions potentially impairing gastrointestinal function—such as prokinetic agents, enemas, or traditional herbal therapies—are strictly contraindicated.

3.2 Abdominal acupuncture treatment

3.2.1 Instrument Selection

Acupuncture needles were supplied by HanYi (Changchun Aikang Medical Equipment Co., Ltd., Production License No. Jiayao Device Manufacturing Xu 20150075), with specifications of 1.5 cun (0.30 mm × 40 mm) and 2.0 cun (0.30 mm × 50 mm).

3.2.2 Acupoint Selection

Acupoint selection for abdominal acupuncture was based on Abdominal Acupuncture Therapy¹⁴:

Primary points: Zhongwan (CV12), Xiawan (CV10), Qihai (CV6), Guanyuan (CV4), and bilateral Daheng (SP15).

Secondary points: bilateral Huaroomen (ST24) and Wailling (ST26).

3.2.3 Point Localization

Point localization was standardized according to the *National Standard of the People's Republic of China (GB/T 12346-2021): Nomenclature and Location of Acupuncture Points*. The anatomical positions include: Zhongwan (CV12), Xiawan (CV10), Qihai (CV6), Guanyuan (CV4), Daheng (SP15), Huaroomen (ST24), and Wailling (ST26) (Figure 2).

[figure not shown]

Figure 2 Abdominal divine turtle diagram and selected acupoints.

The acupoints marked with red dots indicate the sites selected for treatment in this study.

3.2.4 Procedure

Patients were placed in the supine position with the abdominal region fully exposed. Acupoint selection and needling techniques followed the standards outlined in *Abdominal Acupuncture Therapy*. For localization: the distance from the umbilicus (CV8) to Zhongting (CV16) was defined as 8 cun above the navel; from the umbilicus to the pubic symphysis was defined as 5 cun below the navel; and the transverse distance from the umbilicus to the lateral abdominal margin was defined as 6 cun. All acupoints were measured precisely with a straight ruler and proportionally located. After strict hand hygiene and aseptic preparation of the acupoint sites,

routine skin disinfection was performed. Disposable sterile acupuncture needles were inserted perpendicularly. Care was taken to ensure minimal or no pain during insertion. Needle manipulation employed gentle rotational techniques without lifting or thrusting. Primary acupoints were needled to the *Di level* (deep layer, at the base of subcutaneous fat or on the fascia, insertion depth approximately 1.0–1.5 cun), primarily for treating visceral disorders. Secondary acupoints were needled to the *Ren level* (intermediate layer, within the mid-fat tissue, insertion depth approximately 0.5–1.0 cun), predominantly for stimulating peripheral systems. Needle depth was adjusted according to body habitus, and patients were not required to experience the typical *deqi* sensations of soreness, numbness, distension, or heaviness.

Needles were retained for 30 minutes, during which an infrared therapeutic lamp was applied for concurrent warming therapy. After treatment, needles were withdrawn carefully, and sterile cotton was applied with gentle compression at the insertion sites to prevent bleeding.

Note: Needling was avoided directly at surgical incisions. In such cases, acupoints were either slightly displaced for adjusted localization or omitted as appropriate.

3.2.5 Treatment Course

The first abdominal acupuncture session was performed 4–6 hours postoperatively. From postoperative Day 1 through Day 4, one session was administered daily, with a total of five sessions constituting a complete treatment course. Clinical condition was carefully documented and evaluated throughout and following the treatment period.

4. Outcome Measurements

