2.4.2.5 Dropout Criteria

- (1) Patients who develop subcutaneous hematoma, skin damage, or rash at the primary acupoint sites during the trial, rendering acupuncture infeasible;
- (2) Patients who fail to comply with the prescribed treatment protocol or have incomplete data.

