4.1 General Parameters

Collected variables included age, body mass index (BMI), intraoperative blood loss, operative duration, and length of postoperative hospitalization.

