4.3 Efficacy Parameters

4.3.1 Clinical efficacy indices

- **Recovery of gastrointestinal motility** including time to first postoperative passage of flatus (recorded to the exact hour and minute), time to first postoperative bowel movement (recorded precisely), and restoration of bowel sounds.
- **Incidence of postoperative gastrointestinal dysfunction** related complications: including abdominal distension or pain, nausea, vomiting, and diarrhea.

All the above parameters were observed starting on the day of surgery and continued to be

recorded daily until the fifth postoperative day or discharge, whichever came first.

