4.3.2 Laboratory Parameters

Inflammatory markers included C-reactive protein (CRP), serum interleukin-6 (IL-6), serum tumor necrosis factor- α (TNF- α), and the systemic immune-inflammation index [SII, SII = (platelet count \times neutrophil count) / lymphocyte count].

Each parameter was assessed once preoperatively, on the day of surgery prior to treatment, and on postoperative Day 5.

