4.3.3 Relevant Assessment Scales

- **Pain assessment:** The Visual analogue scale (VAS) was applied (Appendix 1). Abdominal pain scores were recorded before and after treatment on the day of surgery (5 days after surgery).
- **Gastrointestinal symptom assessment:** Symptom scoring was based on the Perioperative Clinical Evaluation Standards for Gastrointestinal Motility (Guangdong Provincial Standard, Appendix 2). Scores were documented daily from the day of surgery (before treatment) through postoperative Days 1–5, according to observed gastrointestinal function.
- **Quality of life assessment:** The Gastrointestinal Quality of Life Index (GIQLI) was employed (Appendix 3). Assessments were performed on the day of surgery prior to treatment, on postoperative Day 5, and again on Day 14 following the final treatment session.

5. Adverse Events and Management

If adverse reactions occurred during the trial—such as needle stagnation, syncope, breakage, hematoma, or infection—investigators promptly managed the event, ensured patient safety, reassured the participant with an explanation, and documented the details in the case report form.

6. Ethical Principle

This clinical trial was reviewed and approved by the Ethics Committee of Guangdong Provincial Hospital of Traditional Chinese Medicine prior to participant enrollment (Approval No. YF-2023-435-01). The study was conducted in full compliance with the principles of the Declaration of Helsinki.

7. Statistical Analysis

Data were organized and managed using Microsoft Excel to establish a primary database, which was subsequently converted into an SPSS 26.0 database for statistical analysis. The Shapiro–Wilk test was employed to assess the normality of continuous variables. According to data distribution, descriptive statistics were presented as mean \pm standard deviation (SD) for normally distributed variables, and as median with interquartile range [P₂₅, P₇₅] for non-normally distributed variables. Between-group comparisons of normally distributed data were performed using independent-samples t tests, while within-group pre- and post-treatment comparisons were conducted using paired t tests. For non-normally distributed data, the Mann–Whitney U test was applied for between-group comparisons, and the Wilcoxon signed-rank test for within-group comparisons.

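### Early discharge is allowed, but read literally the dropout rule makes a patient who goes home before the Day 4 session or the Day 5 tests a dropout, although her primary outcome is normally already known

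*Protocol*

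**What the plan says.** Four parts of the protocol bear on a patient who goes home early.

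- **Course.** Sections 2.4.3.3 and 3.2.5 start acupuncture 4–6 hours after surgery and continue it to Day 4: "From postoperative Day 1 through Day 4, one session was administered daily, with a total of five sessions constituting a complete treatment course".
- **Observation window.** Under 4.3.1 the clinical efficacy indices, flatus among them, are "recorded daily until the fifth postoperative day or discharge, whichever came first". Discharge before Day 5 is therefore provided for.
- **Fixed Day 5 assessments, both arms.** For the inflammatory markers, 4.3.2 says "Each parameter was assessed once preoperatively, on the day of surgery prior to treatment, and on postoperative Day 5". For the GIQLI, 4.3.3 says "Assessments were performed on the day of surgery prior to treatment, on postoperative Day 5, and again on Day 14 following the final treatment session". The safety tests in 4.2 and the daily symptom score in 4.3.3 also run to Day 5. None of these is limited to one arm, and none carries the discharge proviso of 4.3.1.
- **Dropout rule.** Section 2.4.2.5 lists as dropouts "Patients who fail to comply with the prescribed treatment protocol or have incomplete data". It makes no exception for a patient who leaves because she has recovered.

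Section 2.4.4 adds "The primary outcome measure was the time to first postoperative flatus" and raises the requirement from 33 to 38 per group for 15% dropout or loss to follow-up.

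**The concern.** Each rule is workable alone, but together they do not fit. A discharge that 4.3.1 accepts as a normal end of observation can, under 2.4.2.5, turn the patient into a dropout: through sessions not given (acupuncture arm) or through Day 5 assessments not done (either arm). No section says how she is classed.

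What is at stake is the primary comparison. Early discharge happens after randomization and plausibly follows early bowel recovery, which is what the trial measures. A dropout rule that works through early discharge would select on the outcome. It would also discard flatus times that were fully observed, because of events that come after them.

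**Working it through.** **Step 1. Planned timing of the primary event (2.4.4).** Control mean 37.60 h, SD 4.11 h; expected reduction 8.1 h. Planned acupuncture mean = 37.60 − 8.1 = 29.5 h.

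**Step 2. Is flatus normally known before an early discharge?** Treat flatus time as normal with these means and take P(T > t) = 1 − Φ((t − mean)/SD). The stated SD does not reproduce the stated sample size: 2(1.960 + 1.282)² × 4.11² / 8.1² = 5.4, so 6 per group and not 33. The SD that would give 33 is 8.1 × √(33/21.01) = 10.15 h. That mismatch is a separate matter; both SDs are used here so that the answer does not hang on it.

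| SD | Arm | Flatus still awaited at 48 h | At 72 h |
|---|---|---|---|
| 4.11 h | Control | z = 2.53, 0.6% | about 0 |
| 4.11 h | Acupuncture | z = 4.50, about 0 | about 0 |
| 10.15 h | Control | z = 1.02, 15% | z = 3.39, 0.04% |
| 10.15 h | Acupuncture | z = 1.82, 3.4% | z = 4.19, 0.001% |

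On the plan's own figures, nearly every patient has a known primary outcome three days after surgery. At two days most do, even with the larger SD.

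**Step 3. Apply the rules literally, by day of discharge.** The session count is the most she can have had, with one on the day of surgery and one on each later day.

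| Discharged on | Sessions given (acupuncture arm) | Sessions missed (control) | Day 5 assessments (both arms) | Criterion in 2.4.2.5 that can apply |
|---|---|---|---|---|
| Day 2 | at most 3 of 5 | none prescribed | not done unless she returns | acupuncture: both limbs; control: incomplete data |
| Day 3 | at most 4 of 5 | none prescribed | not done unless she returns | acupuncture: both limbs; control: incomplete data |
| Day 4, after the session | 5 of 5 | none prescribed | not done unless she returns | both arms: incomplete data |

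The two limbs overlap. Anyone who leaves before the Day 4 session also leaves before Day 5. The missed-session limb therefore adds exclusions of its own only where the Day 5 data are still obtained after discharge. In that case a control with the same discharge day is complete and the acupuncture patient is not.

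**Step 4. Do dropouts leave the analysis?** No section says so. The nearest evidence is the inflation in 2.4.4: 33 × 1.15 = 37.95, which rounds to the stated 38 (33/0.85 = 38.8 would give 39). Raising the number by the dropout rate makes sense if dropouts do not count towards the 33. That suggests exclusion but does not establish it.

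**Step 5. Direction if they do.** Suppose acupuncture shortens recovery and early discharge follows early flatus. Removing early leavers then takes short flatus times from both arms, and more of them from the acupuncture arm, where they are commoner and where the second route operates. The remaining difference tends to be smaller than the true one.

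**Step 6. Size.** The shift depends on the share of patients discharged early in each arm, on how closely early discharge tracks early flatus, and on how many return for Day 5. The protocol gives none of these, no expected stay and no discharge criteria, so no figure is offered.

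**The case against.** The case against has real force, and several parts of it stand.

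- **Discharge before Day 5 is not forecast.** Section 4.3.1 only allows for it, and the fixed Day 5 assessments suggest that most patients were thought to be available then. This stands. The problem may be rare.
- **A patient sent home recovered has not plainly failed to comply.** This is a fair reading of the first limb, but it leaves the second untouched: her Day 5 data are still incomplete unless she returns.
- **Exclusion is not stated, and analysis sets may be defined in a statistical analysis plan.** This stands, and the point on bias is conditional for that reason. The conflict between course, window, assessments and dropout rule is in the protocol itself.
- **Sessions or tests after discharge are neither planned nor ruled out.** This stands, so dropout is not the only possible outcome.

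A reader might infer more than the text supports. One inference is that the distortion falls on the acupuncture arm alone. It does not: a control discharged before Day 5 can also have incomplete data, and only the missed-session limb is one-sided. Another is that keeping patients in for sessions would distort flatus time. Flatus is planned for Days 1–2, so a longer stay cannot alter it. It could lengthen the stay, but 4.1 lists stay among general parameters and not as an efficacy outcome, and the protocol holds no discharge criteria against which to redefine it.

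**Conclusion.** The point holds as an inconsistency that needs a rule. Sections 2.4.2.5, 2.4.3.3, 3.2.5, 4.2 and 4.3.1–4.3.3 do not agree on the status of a patient discharged before the Day 4 session or the Day 5 assessments. Read literally, a fast-recovering patient in either arm becomes a dropout although her primary outcome is normally in hand.

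The consequence for the flatus comparison rests on two assumptions: that dropouts are left out of the analysis (suggested by the step from 33 to 38, stated nowhere) and that early discharge goes with early flatus (plausible, not documented). If both hold, exclusion depends on recovery after randomization and tends to bias the comparison towards no effect. The size cannot be determined from the protocol. Any figure for it would rest on discharge shares and correlations that have no source in the document.

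**What to change.** Reconcile 2.4.2.5 with 2.4.3.3, 3.2.5, 4.2 and 4.3.1–4.3.3 by adding a statement with three parts:

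1. Discharge before the Day 4 session or before the Day 5 assessments is recorded as such in either arm, with the discharge date and, in the acupuncture arm, the number of sessions given.
2. It is not by itself a dropout under 2.4.2.5.
3. The patient's time to first flatus is analysed in her allocated arm.

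This settles how patients are classified and analysed. It does not set when patients should be discharged or how many sessions they should receive; those remain for the investigators.

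The cost is a few sentences and a field on the case report form. The small downside is that the acupuncture arm will include patients with fewer than five sessions, so the comparison describes the course as delivered up to discharge. Because flatus is planned at about 29.5 h in that arm, the later sessions could in most patients not have influenced the primary outcome anyway.
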